TITLE	Anatomical feasibility of an off-the-shelf scalloped stent-graft for infrarenal abdominal aneurysm with a hostile neck (ReSTHoNe study)
PARTECIPATING CENTERS AND INVESTIGATORS	Coordinator centre: AOU di Modena, Main investigator [name] (UNIMORE). Other investigators: [name] (AOU), [name] (AOU), [name] (UNIBO), [name] (UNIBO), [name] (UNIBO) and [name] (UNIBO).
RATIONAL	Endovascular aneurysm repair (EVAR) is currently accepted as the preferred choice to treat the abdominal aortic aneurysms (AAA) with a feasible anatomy ^{1,2} . Although approximately 40-60% of AAA patients are not considered anatomically feasible for EVAR, mainly in reason of a “hostile neck anatomy” ³⁻⁵ . In “real-world” clinical practice, up to 44% of EVAR cases are performed outside Instruction For Use (IFU) for adverse neck anatomy ⁶ . The off-label use of standard EVAR is currently used for patients who are not eligible for OR, with acceptable short- and mid-term outcomes, but the long-term durability of EVAR depends on the maintenance of the seal between the endograft and the aortic neck as well as the iliac arteries ⁷ . Some aortic neck characteristics contribute in the definition of “hostile neck,” particularly length shorter than 15

	
mm and angulation among others⁸. From a recent Consensus Conference, the influence of each characteristic on early or late EVAR failure is not clear, but hostile neck morphology is generally associated with higher rates of aneurysm-related adverse events and mortality⁹. A recent independent Expert Panel, applying the Delphi methodology Indeed, agreed to define 10 mm as the threshold value below which standard EVAR should not be considered feasible⁹. Moreover, the same experts agreed on the fact that an angulation above 60° is considered a hostile criterion for EVAR procedure. Finally should be considered that some “hostility” factors can be present at the same time and creating the ideal condition for EVAR failure⁹. The issue linked to the anatomical not feasibility of standard EVAR in patients not eligible for OR can be solved with custom made devices (CMD), but they were limited by high production costs and long time for creations (10-12 weeks)¹⁰. Nowadays no one off-the-shelf device aimed to overcome neck hostility in AAA is available on the market.
 
The present study aims at evaluating the anatomical applicability of an off-the-shelf scalloped stent-graft (Treovance, Terumo Aortic) to treat infrarenal AAA with a short and/or angulated neck.

Schedule	
Step 1: Ex-Vivo phase
 
 - Step 1.0: Protocol proposal and CE approval - Step 1.1: CTA measurement - Step 1.2: CTA data analysis - Step 1.3: Models fitness evaluation

	
 - Step 1.4: Preliminary publication and endograft production
STUDY DESIGN	Step 1-Single center retrospective observational study on the anatomical applicability in the coordinator center of an off-the-shelf scalloped device to treat infrarenal AAA with short and/or angulated neck.
EX VIVO AND IN VIVO TREATMENT	
Step 1: All patients affected by AAAs and electively treated with EVAR or OR in the Vascular Surgery Unit of Modena e Reggio Emilia from 2010 to 2020 were considered eligible for the ex-vivo feasibility study. Preoperative contrast-enhanced computed tomography scans (CTAs) were independently reviewed by 2 vascular surgeons (investigators) experienced in the planning of aortic procedures using a dedicated workstation with dedicated vascular software (EndoSize, Thereva). Multiplanar and curved reconstructions of each CTA were used to assess the required measurements. In addition to standard measurement taken to plan an EVAR procedure the center-lumen-line distance from the inferior margin of the upper renal artery to the inferior margin of the lower renal artery was taken in order to estimate the gain of neck length permitted with the scallop. An inter-examiner or intra-examiner error of 5% was accepted. In case of a variation >5%, a third investigator of the study would independently reanalyze the CTA. To study the suitability of the device, 2 different endograft models were constructed and fitted in the CTA-based

	measurements made as described to evaluate the anatomical feasibility of these models.
INCLUSION CRITERIA	
Step 1:
 
 - Patients Electively treated with EVAR or AAA at the coordinator center - Age >18 -Both sex -Preoperative 2.5mm CTA available -Written informed consent.
SAMPLE SIZE	Step 1: No statistical analysis of the sample size was carried out. Considering the number of AAA treated in the coordinator center each year and analyzing a time interval of 10 years a sample size of 1000 CTA was estimated. This number should be sufficient to carry out the anatomical feasibility analysis.
OUTCOMES/ENDPOINTS	
Step 1
 
Outcome: Anatomical feasibility evaluation

STATISTICAL ANALYSIS	To study the suitability, 2 different endograft designs were constructed. The preoperative measurements were made according to a previously described methodology. The models were matched with each preoperative CTA measure in order to evaluate if they fit or not in the index patients. Continuous variables are expressed as mean, and standard deviation and

	
differences were tested with the two-sided t-test or the Mann-Whitney U-test, if appropriate. Categorical variables are expressed as counts and percentages and the chi-square test or Fisher's exact test was used for analysis. All data were entered into the logistic regression model if they had a univariable P-value of <0.05. Data resulted significant in this model were put in a multivariate one. In the multivariable analyses, clinical factors or potential confounding variables were expressed as odds ratio with 95% confidence interval (CI). The goodness of fit of the logistic regression models has been assessed calculating the C-statistic.. The analysis was carried out using STATA 14.

REFERENCES	

- | | |
|--|---|

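### The planned fit rate will not separate patients gained by the scallop from those the same graft would already fit without it

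*Combined protocol and SAP*

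**What the plan says.** The Rational section states the aim: "The present study aims at evaluating the anatomical applicability of an off-the-shelf scalloped stent-graft (Treovance, Terumo Aortic) to treat infrarenal AAA". The necks that the aim has in view are short, angulated or both. The section motivates the device by the limits of standard EVAR: "Although approximately 40-60% of AAA patients are not considered anatomically feasible for EVAR", mainly because of the neck. It counts a neck length under 15 mm among the hostile features, and reports that an expert panel "agreed to define 10 mm as the threshold value below which standard EVAR should not be considered feasible".

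Under Ex vivo and in vivo treatment, all AAA patients treated electively by EVAR or open repair from 2010 to 2020 are eligible, with no hostile-neck criterion. Measurement is described as follows: "In addition to standard measurement taken to plan an EVAR procedure", the centre-lumen-line distance between the lower margins of the upper and lower renal arteries "was taken in order to estimate the gain of neck length permitted with the scallop". Then: "To study the suitability of the device, 2 different endograft models were constructed and fitted in the CTA-based" measurements. Neither model is described further.

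The Outcomes/Endpoints entry reads, in full for Step 1, "Outcome: Anatomical feasibility evaluation". The Statistical analysis section gives the scoring: "The models were matched with each preoperative CTA measure in order to evaluate if they fit or not in the index patients". It names t, Mann-Whitney, chi-square and Fisher tests and logistic regression. It contains no numerical fit rule, no with/without comparison and no paired analysis.

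**The concern.** The argument for the device is incremental: standard EVAR does not suit many necks, and a scallop might extend the usable seal. The extra renal measurement shows that the investigators want to know that gain. But nothing in the plan turns millimetres gained into patients gained.

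A CTA therefore counts as a fit whether or not the scallop did anything. Two examples are a neck that already meets the length rule and a pair of renal arteries at the same level, where the gain is zero. With all elective cases eligible, including those treated by EVAR, such CTAs should be common. A reader who sees a high fit percentage for a scalloped graft will tend to credit the scallop, and the planned analysis gives no means of checking that.

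**Working it through.** **No plan figure to reproduce.** The documents give no expected fit rate or expected gain. The only size is 1000 CTA, taken from centre volume over 10 years (1000 / 10 = 100 per year implied; the annual volume is not stated).

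**1. A fit rate alone does not identify the gain.** If 40-60% of patients are not feasible for standard EVAR, 40-60% are feasible. I use this as a stand-in for the same graft without its scallop. Net gain = scalloped fit rate minus unscalloped fit rate. For assumed scalloped fit rates:

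- 60%: 60 - 60 = 0 to 60 - 40 = 20 points
- 70%: 70 - 60 = 10 to 70 - 40 = 30 points
- 80%: 80 - 60 = 20 to 80 - 40 = 40 points

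At each assumed fit rate, the gain is left open over a 20-point range.

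**2. Does a hostile-neck subset solve it?** Hostile on length is under 15 mm; the standard-EVAR limit is 10 mm. A neck of 10 to under 15 mm is thus hostile and yet, on length, may already suit a standard graft. A subset under 10 mm would solve it on length, since unscalloped fit is then 0% by definition. But it would leave out necks of 10 mm or more that are angulated, which the aim also names.

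**3. Illustration of size (all inputs assumed).** Neck length L is log-normal with log-SD 0.7 and median M = 10 or 12 mm. The inter-renal distance is 0 in 30%, and otherwise exponential with mean m = 3, 6 or 9 mm, independent of L. Fit means at least 10 mm of length; angulation is ignored. The 10 mm is used only because it is the one standard-EVAR length limit in the documents.

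- Fit without scallop = 1 - F(10), where F(x) = Φ[(ln x - ln M)/0.7] and f is its density.
- Increment = 0.7 × ∫₀¹⁰ f(x) exp[-(10 - x)/m] dx.
- Fit without scallop among necks under 15 mm = [F(15) - F(10)] / F(15).

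| Median neck | Fit without | Fit with (m = 3 / 6 / 9) | Increment, points | Under 15 mm: fit without |
|---|---|---|---|---|
| 10 mm | 50.0% | 62.6 / 69.8 / 73.6% | 12.6 / 19.8 / 23.6 | (0.7188 - 0.5000)/0.7188 = 30.4% |
| 12 mm | 60.3% | 71.1 / 76.8 / 79.6% | 10.9 / 16.5 / 19.4 | (0.6251 - 0.3973)/0.6251 = 36.4% |

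These medians were chosen so that unscalloped fit is about 50-60%, in line with the rationale. A 15 mm median would give 72%, above that range, so I do not rely on it.

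**4. Precision of the proposed result.** Let b be the share fitting only with the scallop. If the scallop only adds length, no CTA fits without it and fails with it, so b is also the paired difference. Half-width = 1.96 × √[b(1 - b)/N]. At N = 1000:

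- b = 5%: 1.96 × √(0.05 × 0.95/1000) = 1.35 points
- b = 10%: 1.86 points
- b = 20%: 2.48 points

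If some CTAs could fit only without the scallop (share c), the half-width for d = b - c is 1.96 × √[(b + c - d²)/N]. For b = 20% and c = 5% this is 2.96 points. The planned sample is adequate; the gap is in the endpoint and its analysis.

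**The case against.** The strongest reply is that the stated aim is applicability, not added benefit, and a fit rate answers that question. This stands in part. It is a reason to report the scallop-only percentage beside the fit rate and not in its place.

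Second, much of the mixing comes from the all-comers denominator, which a suitable subset could remove. That holds on length for necks under 10 mm. It does not hold for necks under 15 mm, and the plan defines neither subset for analysis.

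Four stronger readings are tempting, and the documents do not support them:

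- *Both models are scalloped.* This is the natural reading of a study of this device, but the text never says so. One model could be an unscalloped comparator; if so, the plan would still need to say it and specify the paired contrast.
- *The study cannot show what the scallop adds.* The standard EVAR measurements and the inter-renal distance are taken on the same CTAs, so the comparison can be derived once a fit rule is fixed. What is missing is its prespecification.
- *A misleading fit rate would drive production.* Step 1.4 lists preliminary publication and endograft production together, but no threshold or go/no-go rule links production to the fit rate.
- *Most of the fit rate owes nothing to the scallop.* That is so in the illustration, but it follows from assumed inputs. No fit has been reported.

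**Conclusion.** The concern holds in limited form. The plan does not prespecify a same-CTA fit without the scallop, so its fit rate will not show how many patients the scallop gains. No other section repairs this.

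The size is not known from the documents. With the assumptions above, the increment is about 11-24 points on an unscalloped base of 50-60%, and about 30-36% of necks under 15 mm fit without the scallop. Those figures depend on the assumed neck-length and inter-renal distributions, on their independence, and on a length-only rule. The qualitative conclusion needs only that some analysed necks would fit without the scallop, which the rationale's own 40-60% makes likely in an unrestricted elective series. The change should be made, but it does not undermine the data collection or the sample size.

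**What to change.** 1. Describe both models and say whether each carries a scallop. State the fit rule in numbers before the models are matched to the CTAs.
2. For each scalloped model, apply that same rule to each CTA twice: once with the scallop gain and once with the gain set to zero.
3. Report the percentage that fit only with the scallop, with a 95% CI, alongside the overall fit rate. Give both in all patients and in the short and/or angulated necks that the aim names, with that subset defined in advance.
4. If the rule allows a CTA to fit only without the scallop, report that share too and analyse the difference as paired (McNemar), since the chi-square and Fisher tests named in the plan are for independent groups.

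The cost is protocol wording and one extra derived variable per scalloped model; no new imaging or patients are needed. The small downside is a less favourable figure printed beside the raw fit rate.

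### Does the 5% reader-agreement rule, set against 2.5 mm scans, leave the fit / no-fit count unprotected?

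*Combined protocol and SAP*

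**What the plan says.** Under EX VIVO AND IN VIVO TREATMENT, the preoperative scans "were independently reviewed by 2 vascular surgeons (investigators) experienced in the planning of aortic procedures", on dedicated vascular software. On technique, the section adds: "Multiplanar and curved reconstructions of each CTA were used to assess the required measurements". Beyond the usual EVAR planning measurements, the readers take the "center-lumen-line distance from the inferior margin of the upper renal artery to the inferior margin of the lower renal artery", which estimates how much neck length the scallop gains. The agreement rule reads: "An inter-examiner or intra-examiner error of 5% was accepted. In case of a variation >5%, a third investigator of the study would independently reanalyze" the scan.

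INCLUSION CRITERIA requires "Preoperative 2.5mm CTA available". RATIONAL cites an expert panel that "agreed to define 10 mm as the threshold value below which standard EVAR should not be considered feasible". It also mentions 15 mm and 60° as markers of a hostile neck. Under STATISTICAL ANALYSIS, two endograft designs are matched to each scan's measurements to see whether they fit.

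The plan gives no absolute tolerance, no denominator for the percentage, no rule for turning two or three readings into one value, and no cut-offs for the two models.

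**The concern.** A purely relative limit shrinks with the length measured, and this study is about short necks. Near 10 mm it asks for agreement well below the slice thickness. For the inter-renal distance, the measurement specific to the scallop, it tends to zero and cannot be computed when the renal arteries are level.

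The rule also takes no account of the endpoint, which is binary. Two readings can agree within 5% and still lie on opposite sides of a fit cut-off, and nothing then calls in the third investigator. The plan does not say which value is analysed. An intra-examiner limit is stated, but no repeat reading is described.

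If these effects were large, the third investigator would be busy with measurement noise while the borderline scans passed unexamined, and the feasibility percentage would depend on whose reading was used.

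**Working it through.** The plan gives no agreement or reader-error figure, so there is nothing to reproduce.

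**Inputs from the documents.** Limit 5%; scans 2.5 mm (taken as slice thickness); illustrative markers 10 mm, 15 mm and 60°.

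**Assumptions.** Independent normal reader errors without systematic bias. Per-reader SD 0.25 to 2.0 mm; an error uniform over one slice would give 2.5/√12 = 0.72 mm. For the simulations, true necks uniform on 5 to 15 mm and a 10 mm cut-off.

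**1. Tolerance against resolution.** Tolerance = 0.05 × length.

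| Length | 5% of length | Share of 2.5 mm | One slice as % of length |
|---|---|---|---|
| 5 mm | 0.25 mm | 10% | 50% |
| 10 mm | 0.50 mm | 20% | 25% |
| 15 mm | 0.75 mm | 30% | 17% |

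A one-slice difference passes only from 2.5/0.05 = 50 mm upward.

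**2. Chance of a third read.** P = 2 × [1 − Φ(0.05L / (SD × √2))].

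| Length | SD 0.3 mm | SD 0.5 mm | SD 0.72 mm | SD 1.0 mm |
|---|---|---|---|---|
| 5 mm | 56% | 72% | 81% | 86% |
| 10 mm | 24% | 48% | 62% | 72% |
| 15 mm | 8% | 29% | 46% | 60% |

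Whether most scans are re-read therefore turns on an SD that the documents do not give.

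**3. Zero and small distances.** Readings of 0 and 0 give 0/0, but they agree exactly and nothing needs settling. Readings of 0 and 1 mm differ by 200% of the mean or 100% of the non-zero reading; only dividing by the zero reading leaves the ratio undefined. At 2 mm the tolerance is 0.1 mm, so small distances tend to be re-read.

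**4. Accepted pairs that straddle a marker.** 9.8 and 10.2 mm: 0.4/10.0 = 4.0%. 14.7 and 15.3 mm: 0.6/15.0 = 4.0%. 59° and 61°: 2/60 = 3.3%. All pass. In simulation, the share of scans that are discordant at 10 mm and not re-read is:

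| SD | Discordant, not re-read |
|---|---|
| 0.25 mm | 1.8% |
| 0.5 mm | 1.2% |
| 1.0 mm | 0.7% |
| 2.0 mm | 0.35% |

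**5. Effect on the result.** Take the mean of two agreeing readings and the median of three otherwise. Adding a third read for every discordant pair lowers misclassification by about 0.06 to 0.15 percentage points; at SD 0.5 mm it goes from 2.82% to 2.67%. The feasibility percentage moves by less than 0.02 points.

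The uniform 5 to 15 mm range is symmetric about the cut-off, which helps errors cancel. A bound that does not need cancellation is the discordant share itself: calling every such pair a fit, or none of them, shifts the percentage by at most 1.8 points between the two extremes at the SDs tabulated.

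**6. The alternative tolerance.** A one-slice limit of 2.5 mm would call a third read with probability 2 × [1 − Φ(2.5 / (SD × √2))]: 0.04% at SD 0.5 mm, 1.4% at 0.72 mm and 7.7% at 1.0 mm. It would accept a 25% disagreement at 10 mm.

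**The case for a change.** The strongest case for a change is that the rule is strict where strictness adds little and has no trigger where the endpoint is decided. A straddling window exists at any positive cut-off, so the missing model cut-offs do not remove it. The silence on the final value affects every re-read scan, not only the borderline ones. The remedy would be a few words and would use the readers already named.

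The structural observation stands: the 5% rule does not refer to fit, and the plan does not say how readings are combined. The rest is weaker.

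- Re-reading too often is cautious; it costs time and loses no protection.
- Slice thickness does not cap agreement, since both readers work on the same scan with multiplanar and curved reconstructions and can place points between slices.
- The 10 mm example straddles a value for standard EVAR. The scallop is meant to add usable length, so the example does not show a documented disagreement on fit.
- Naming an intra-examiner limit suggests that repeat reads were intended. Deleting it would remove a check.
- A one-slice tolerance would nearly end third reads for lengths, although those lengths are also summarised and tested as continuous variables.
- Bland-Altman limits and kappa are reporting preferences. How the scan criterion is worded for thinner slices is a separate clarification.

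**Conclusion.** No change is needed. The arithmetic behind the concern is right, but its consequence for the result is negligible: less than 0.02 percentage points on the feasibility percentage and 0.06 to 0.15 points on misclassification. Following the plan as written, with the ordinary mean of two or median of three, leads to the same conclusion. The tight limit is a fair trade of reader time for caution, and replacing it with a one-slice limit would be no clear improvement.

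This rests on unbiased, independent reader errors with SDs of 0.25 to 2.0 mm, an illustrative 10 mm cut-off and true necks of 5 to 15 mm. The documents supply neither the reader error nor the models' cut-offs. A systematic difference between readers, or cut-offs in a dense part of the neck-length distribution, would make the effect larger than simulated.

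### Both endograft models are tried on the same CTAs: does the plan need a paired test that it does not name?

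*Combined protocol and SAP*

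**What the plan says.** The EX VIVO AND IN VIVO TREATMENT section states that "2 different endograft models were constructed and fitted in the CTA-based" measurements. STATISTICAL ANALYSIS repeats the step: "The models were matched with each preoperative CTA measure in order to evaluate if they fit or not in the index patients". Each CTA is thus judged twice, once per model, with a yes/no result each time.

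For testing, the same section says of continuous variables that "differences were tested with the two-sided t-test or the Mann-Whitney U-test, if appropriate". It then says "Categorical variables are expressed as counts and percentages and the chi-square test" or Fisher's exact test is used. The next step is "All data were entered into the logistic regression model if they had a univariable P-value of <0.05", followed by a multivariable model reported as odds ratios with 95% confidence intervals.

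OUTCOMES/ENDPOINTS has one entry, "Outcome: Anatomical feasibility evaluation". SAMPLE SIZE says "No statistical analysis of the sample size was carried out" and that "a sample size of 1000 CTA was estimated" from the caseload over 10 years. The documents give no fit rate, no between-model correlation and no hypothesis that sets one model against the other.

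**The concern.** Two yes/no results on the same anatomy are very likely to be correlated: a neck that defeats one model will often defeat the other. Chi-square and Fisher's exact tests assume that the two proportions come from different patients. If an analyst put the two fit rates into a 2x2 table of model by fit, each CTA would be counted twice and the correlation ignored. The right tool for that question is McNemar's test with an interval for the paired difference, and the plan names neither.

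Two things would be at stake. A modest real difference between the designs could be missed. And if only two separate percentages were reported, the reader could not tell what share of patients is fitted by at least one model. Because the Schedule moves from evaluating the models to endograft production, both questions could naturally arise.

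**Working it through.** **Inputs from the documents.** Two models; the same CTAs for both; 1000 CTAs planned. The 1000 cannot be re-derived: it rests on annual caseload, which is not given (1000 over 10 years implies about 100 a year).

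**Inputs assumed.** Fit rates p1 = 50% and p2 = 53%, and within-CTA correlation ρ from 0.25 to 0.9.

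**Standard errors.** Let v = p(1 − p), so v1 = 0.25 and v2 = 0.53 × 0.47 = 0.2491.

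- Unpaired: √[(v1 + v2)/n] = √(0.4991/1000) = 2.23 points.
- Paired: √[(v1 + v2 − 2ρ√(v1v2))/n], with √(v1v2) = 0.24955. At ρ = 0.5 this is √(0.24955/1000) = 1.58 points.
- With equal fit rates the ratio reduces to 1/√(1 − ρ), whatever n is.

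**P values at 50% v 53%, no continuity correction.** Chi-square: 0.03² / (2 × 0.515 × 0.485/1000) = 1.80, P = 0.18, whatever ρ is. McNemar: (c − b)²/(b + c), where b and c are the discordant counts. At ρ = 0.5 this is (140 − 110)²/250 = 3.60, P = 0.058.

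| ρ (assumed) | Paired SE, points | Unpaired/paired SE | Discordant counts | McNemar P |
|---|---|---|---|---|
| 0.25 | 1.93 | 1.15 | 173 v 203 | 0.12 |
| 0.5 | 1.58 | 1.41 | 110 v 140 | 0.058 |
| 0.75 | 1.12 | 2.00 | 48 v 78 | 0.008 |
| 0.9 | 0.71 | 3.16 | 10 v 40 | <0.001 |

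**Limit on the top row of ratios.** The largest attainable correlation, for p1 < p2, is √[p1(1 − p2)/(p2(1 − p1))]. At 50% v 60% it is √(0.20/0.30) = 0.816, so the ratio cannot exceed about 2.3. At 40% v 60% it is 0.667, with a ratio of about 1.7. The figure of 3.2 needs nearly equal fit rates.

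**Direction.** The true type I error of a nominal 5% unpaired test is 2Φ(−1.96/√(1 − ρ)): 2.4% at ρ = 0.25, 0.6% at 0.5 and under 0.01% at 0.75. The error is conservative.

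**Power with n = 1000, chi-square v McNemar.**

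- 3 points (50% v 53%), simulated: 24% v 34% at ρ = 0.25; 20% v 47% at 0.5.
- 5 points (50% v 55%), normal approximation: 63% v 73% at ρ = 0.25; 65% v 89% at 0.5.
- 10 points (50% v 60%), simulated: both above 99% for ρ from 0.25 to 0.8.

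**Share fitted by at least one model.** This is p1 + p2 − p11, with p11 = p1p2 + ρ√(v1v2). At 50% and 53% it is 70.3% for ρ = 0.25 and 54.0% for ρ = 0.9. The margins alone allow 53% to 100%, but 100% would need p11 = 0.03, that is ρ = (0.03 − 0.265)/0.24955 = −0.94. Such a strong negative correlation is implausible for two devices judged on the same neck.

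**What the tests are for.** The section names the t-test and Mann-Whitney U-test, then chi-square and Fisher's exact, then the entry rule for the logistic model. The continuous data described are patient measurements, which take the same value whichever model is being fitted, so those tests cannot be contrasting the models. They must contrast groups of patients, and the categorical tests sit beside them in the same role. Whether the groups are fit v no fit or EVAR v open repair, they are different people, and independent-samples tests are suitable.

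**The case for a change.** The strongest case for a change is that a plan with two designs and production as the next step will hardly avoid asking which design fits more patients, or how many are covered by the pair. If that is asked, the only categorical tests on the page are the wrong ones, and one or two sentences with no new data would close the gap. The power loss is also real in a narrow band: at an assumed ρ of 0.5, a 5-point difference has 65% power instead of 89%.

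The facts behind this stand: the results are paired, no paired method is named and the arithmetic is right. What does not stand is the step from silence to error. The plan sets no model-against-model test, so it assigns no wrong test to one. The reading of the listed tests as a univariable screen is an inference, since the logistic outcome is not spelled out, but it is the only reading under which the continuous tests make sense. The missing cross-table is not lost information either. Both fit results are produced for each CTA, and the plan lists no output tables of any kind, so the absence of this one means little.

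**Conclusion.** No change to the plan is called for. Followed as written, the plan yields a fit proportion for each model and a comparison of independent patient groups, and neither is affected by the pairing. The standard-error inflation attaches only to a comparison that the plan does not contain. Its size depends wholly on assumed inputs: a factor of 1.15 to 1.41 for ρ of 0.25 to 0.5, at most about 2.3 at 50% v 60%, and near 3.2 only when the fit rates almost coincide and ρ is 0.9. Given positive correlation, it could hide a small difference but not invent one.

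This is a gap that an analyst fills sensibly. Anyone who decides to compare the designs would cross-tabulate the two results, use McNemar's test with a paired interval, and read the either-fits and neither-fits shares from the same table. The conclusion would differ if the sponsor stated a model-against-model hypothesis and tied it to chi-square or Fisher's exact test; nothing in the documents does so.

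### Covariates are screened on significance twice and then reported with ordinary 95% CIs, so weak or null effects that survive can look stronger and more certain than they are

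*Combined protocol and SAP*

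**What the plan says.** The STATISTICAL ANALYSIS section first compares variables one at a time. For continuous data, "differences were tested with the two-sided t-test or the Mann-Whitney U-test, if appropriate"; categorical data get a chi-square or Fisher's exact test. Two selection steps follow.

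- First filter: "All data were entered into the logistic regression model if they had a univariable P-value of <0.05".
- Second filter: "Data resulted significant in this model were put in a multivariate one".

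The results are then reported: "In the multivariable analyses, clinical factors or potential confounding variables were expressed as odds ratio with 95% confidence interval (CI"). The only model check is discrimination on the same data: "The goodness of fit of the logistic regression models has been assessed calculating the C-statistic".

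The plan contains no covariate list fixed in advance, no variable forced into the model, no penalisation, no bootstrap or validation, and no allowance for selection in the intervals. It does not name the dependent variable of the regression. The only listed outcome is anatomical feasibility.

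**The concern.** An ordinary 95% CI assumes that the model was chosen without looking at the outcome. Here a term is reported only because its estimate was far enough from zero to be significant. For a weak true effect, the runs that pass are those in which chance pushed the estimate outward, so the reported odds ratio is too large on average. A variable with no effect passes only when chance made it look real, so its interval will usually exclude 1. The C-statistic, computed on the same data, cannot reveal either problem.

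These odds ratios are the only results for which the plan specifies a CI. What is at stake is whether the list of factors associated with the outcome, and the precision attached to it, can be taken at face value.

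**Working it through.** **Inputs from the plan.** Screening at P<0.05, two-sided for the t-test; a second filter on significance (0.05 is inferred); about 1000 scans. There is no power figure to reproduce. The SAMPLE SIZE section says "No statistical analysis of the sample size was carried out", and the 1000 is a volume estimate.

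**Assumed inputs (not in the plan).** 15 standardised candidates, 5 with true OR 1.15 per SD and 10 null; outcome present in 50%; pairwise correlation 0 or 0.3. Two readings are tested. In the *joint* reading the first logistic model contains all screened variables, and the significant ones are refitted. In the *univariable* reading the first logistic model takes variables one at a time, so the second filter nearly repeats the first.

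**Step 1: false entries at the first filter.** With 10 independent null candidates, the chance of at least one entry is 1 − 0.95^10 = 40.1%. With 20 it is 1 − 0.95^20 = 64.2%.

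**Step 2: expected exaggeration, uncorrelated.** The SE of a log OR per SD is about 1/√(1000 × 0.5 × 0.5) = 0.0632. Significance needs an estimate above 1.96 × 0.0632 = 0.124, that is OR 1.13. The true value is ln 1.15 = 0.1398, so z = 0.1398/0.0632 = 2.21 and the chance of passing is Φ(2.21 − 1.96) = Φ(0.25) = 0.599. The mean estimate given passing is 0.1398 + 0.0632 × φ(0.25)/Φ(0.25) = 0.1398 + 0.0632 × 0.3867/0.599 = 0.181, that is OR 1.20.

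**Step 3: correlation 0.3, joint reading.** The variance inflation is (1 + 13 × 0.3)/(0.7 × (1 + 14 × 0.3)) = 4.9/3.64 = 1.35, so the SE is 0.0632 × √1.35 = 0.0734. The threshold is 1.96 × 0.0734 = 0.144, or OR 1.155. This is just above the true 1.15, so a term must overshoot the truth to pass. The refit can then add to this, because survivors absorb part of the correlated true effects that were dropped.

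**Step 4: correlation 0.3, univariable reading.** A null variable borrows a marginal log OR of about 5 × 0.3 × 0.1398 = 0.21, or z = 0.21/0.0632 = 3.3. Most candidates therefore pass, and the final model is close to the full one.

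**Step 5: simulation at n = 1000, true OR 1.15.**

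| Correlation | First model | Mean surviving OR | Result for intervals |
|---|---|---|---|
| 0 | joint | 1.20 | true effects 95–96% coverage; a null survives in 36–39% of runs, and its CI almost never contains 1 |
| 0 | univariable | 1.20 | CI of a surviving null contains 1 in about 10–15% of cases |
| 0.3 | joint | about 1.28 | true effects 71–73% coverage |
| 0.3 | univariable | 1.14–1.15 | true effects 95% coverage |

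With all 15 kept, coverage is 95%. At true OR 1.25 and correlation 0.3, coverage is 92–94% (joint) or 96% (univariable).

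**Step 6: a different assumed mix.** 13 covariates with true ORs of 1.0 (seven), 1.15 (two), 1.3 (two), 1.6 (one) and 2.0 (one); n = 1000; outcome prevalence 0.5 or 0.2; correlation 0 or 0.3.

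- Joint reading: OR 1.15 is reported as 1.225–1.330 with coverage 80.2–92.3%, and OR 1.3 as 1.315–1.402 with 92.3–97.2%. ORs 1.6 and 2.0 are reported as 1.598–1.661 and 2.001–2.072, with coverage 92.0–96.0%. Surviving nulls have coverage 0.7–24.6%.
- Univariable reading, uncorrelated: OR 1.15 is reported as 1.217–1.256 with coverage 91.8–92.9%. Surviving nulls have coverage 35.3–44.7%.
- Univariable reading, correlation 0.3: every covariate passes and there is no selection effect.
- Full model without selection: coverage 93.1–96.0%, and OR 1.15 is reported as 1.150–1.158.

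**The case against.** The strongest objection is that the size of the problem depends on a reading the plan does not settle. Calling only the later model multivariate suggests that the first logistic model is univariable. On that reading, moderately correlated candidates all or nearly all pass and coverage stays near 95%. This stands: correlation worsens the problem under one reading and removes it under the other, in the settings tried.

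A reader might infer that every surviving odds ratio is biased and every interval misses 95% coverage. The plan does not support that. At about 1000 scans, odds ratios of 1.6 or more are nearly unbiased, and several weaker settings also keep nominal coverage. Much worse figures appear at smaller sizes (at n = 300 and prevalence 0.3, joint reading, OR 1.15 is reported as 1.454–1.583), but that is not the planned size.

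A reader might also infer that real confounders will be screened out. That is possible when one variable masks another, but the plan names no exposure, so there is no defined effect to be confounded.

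It can further be said that if the dependent variable is model fit, some CTA measurements determine it by construction, and weak effects per SD are then a poor description of them. This is fair for those measurements. It does not cover patient characteristics or anatomy outside the fit rule.

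Finally, the regression is tied to no listed outcome, and the proportion of scans that fit is unaffected. That limits the importance of the point but does not justify the rule.

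**Conclusion.** The concern holds in a limited form. The plan selects on significance and reports intervals that ignore the selection, and nothing elsewhere in the document offsets this. At about 1000 scans, and under the assumed inputs, the harm falls on weak and null covariates. A true OR of 1.15 is reported as about 1.20 when candidates are uncorrelated, under either reading, and as about 1.28 with 73% coverage at correlation 0.3 if the first model is joint. Uncorrelated null variables survive in about 36–39% of runs (joint reading), and the CI of a surviving null seldom contains 1. The proportion that do contain 1 varies with the covariate mix: up to about 15% in the 15-candidate setting, and up to about 45% with stronger companion effects and a univariable first model.

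The direction is secure; the size is not. The number of candidates, their effects, their correlation and the event rate are all assumptions. The point concerns the associated-factor analysis only, not the feasibility proportion.

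**What to change.** Replace both screening sentences with:

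> Candidate covariates, comprising patient characteristics and the CTA measurements of interest that do not themselves define model fit, are listed before analysis, entered together in one logistic model, and all reported with 95% CI whatever their P-value. Univariable results are descriptive only.

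Name the dependent variable in the same place, since the list cannot otherwise be separated from the measurements that define fit.

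Do not include the index procedure (EVAR or open repair) as a routine adjuster. The RATIONAL section attributes unsuitability for EVAR mainly to neck anatomy, so the procedure is partly a consequence of the anatomy under study.

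If the list is too long for the number of events, use a penalised model with bootstrap intervals rather than P-value screening.

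The cost is a short list and a few sentences of wording, using data the study already collects. Intervals will be slightly wider and the table will contain some non-significant rows.
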